Specific Aim 2: To explore the adjunctive intervention's acute efficacy in treating emotional distress (anxiety, depression, suicidal ideation, NSSI) and indices of SUD (commitment to sobriety, craving, quantity and frequency of substance use).

Hypothesis 2a. UP participants will evidence greater decreases in Overall Anxiety Severity and Impairment Scale (OASIS) and Overall Depression Severity and Impairment Scale (ODSIS) from pre- to post-treatment than the those in the control condition. Hypothesis 2b. UP participants who report past month suicidal thoughts at baseline will evidence greater reductions in Beck Scale for Suicidal Ideation (BSI⁴⁹) scores from pre-to post-treatment than those in the control condition.

Hypothesis 2c. UP participants who report past month NSSI urges or episodes at baseline will report a lower frequency of NSSI urges and episodes in a one-month period on the Self-Injurious Thoughts and Behaviors Interview-Clinician Rated [SITBI-CR⁵⁰]-

and on the Self-Injurious Thoughts and Behaviors Interview-Self-Rated [SITBI-SR⁵⁰] at post-treatment than the control.

Hypothesis 2d. UP participants will evidence greater increases in Commitment to Sobriety Scale (CSS⁵¹) and decreases in Craving Scale⁵² scores from pre- to post-treatment than the control.

Hypothesis 2e. UP participants will report lower quantity and frequency of substance use during the study period than those in the control condition.

III. SUBJECT SELECTION

We propose to conduct a pilot randomized controlled trial for young adults with SUD and comorbid emotional distress who are entering into or currently engaged in treatment within a comprehensive outpatient program (ARMS at MGH). We plan to enroll 50 young adults (ages 18 to 26) with SUD and comorbid emotional distress from ARMS. They will be randomized in a 2:1 ratio to one of two conditions: 16 twice-weekly sessions of a transdiagnostic, group-based CBT intervention (the Unified Protocol [UP]) plus usual services at ARMS (UP + TAU condition) or treatment as usual at ARMS (TAU; control condition). All potential subjects must satisfy the following inclusion/exclusion criteria upon the study screening visit:

Inclusion criteria:

- 1. Young adults ages 18 to 26, inclusive
- 2. English language proficiency
- 3. Ability to provide written, informed consent
- 4. Ability to attend in-person, outpatient sessions

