measures of anxiety or depression used for clinical purposes at ARMS, and/or report of suicidal thoughts or NSSI in the past week) will be enrolled in the study. An ARMS clinician will determine possible subject eligibility based on information obtained during the routine clinical evaluation for ARMS treatment. Those who are deemed potentially eligible and express interest in the study will then undergo a brief in-person screening visit with a study clinician. The screening visit, which will take about 60 minutes, will consist of a meeting with a study clinician to provide informed consent and confirm study eligibility (via review of information obtained during routine ARMS clinical care and completion of the SITBI-CR). For participants who report suicidal thoughts in the past week or having made a suicide plan or suicide attempt in the past year on the SITBI-CR, a clinical risk assessment (including severity of ideation and presence of plan, intent, and access to means) will be conducted during the visit in order to ensure participant safety and eligibility for the study (i.e., no imminent suicide risk). The study clinician conducting the screening visit will consult the ARMS Clinical Director (or, if [name] is unavailable, another licensed clinician on-site) immediately regarding risk in any questionable cases to determine the appropriate action, per usual ARMS clinical procedures. Eligible participants will then complete the Timeline Follow Back (TLFB^{53,54}) as an interview, in which participants recall the quantity and frequency of substance use during a specified time window (e.g., past month) using a calendar, and several self-report questionnaires, including the BSI, CCS, and Craving Scale (see Table 1). The study clinician will also fill out a concomitant treatment log to identify the participant's overall treatment plan, including medication and therapy. Data obtained at this screening visit will be considered the "pre-treatment" assessment. After eligibility criteria are determined and participants have completed the screening/baseline assessment, participants will be randomly assigned to UP+TAU or TAU only conditions using a permuted block randomization procedure. The permuted block randomization schedules will be generated by an independent biostatistician from the MGH Biostatistics Center prior to enrolling the first subject into the study. Groups, or "blocks," of 5 individuals will be randomized at a time to one of the two treatment conditions (UP+TAU or TAU alone) using a 2:1 randomization scheme, defined as 2 blocks randomized to UP + TAU for every 1 block randomized to TAU alone. Randomizations will be conducted using a web-based randomization program developed by the MGH Biostatistics Center. The randomization code will be generated within the webbased program by study staff only when the randomization occurs, i.e. once the last participant of each group has completed baseline. Participants will then be contacted by study staff via their preferred method of communication to notify them of their study condition.

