TAU condition: After randomization, participants randomized to the TAU condition will undergo usual care at ARMS for the next 8-10 weeks. Usual care at ARMS typically consists of a combination of up to 3 group therapy sessions per week, individual weekly therapy, and/or psychopharmacology appointments as needed. Some ARMS patients are offered and choose to engage in all three treatment modalities (group therapy, individual therapy, and psychopharmacology), whereas others only engage in one treatment modality. No requirements will be placed on TAU participants with regard to TAU dosage and TAU will be consistent with each participant's clinical treatment plan at ARMS; however, TAU attendance (e.g., number of appointments) for all participants will be tracked by study staff. Four to 6 weeks after randomization, TAU participants will complete a mid-treatment assessment, during which they will complete the same self-report questionnaires (plus TLFB and concomitant treatment log with a study clinician) administered at the screening/baseline visit (see *Measures*). Eight to 10 weeks after randomization, they will repeat the same measures for the in-person "post-treatment" assessment. During both the mid- and post-treatment assessments, should a participant report suicidal thoughts in the past week on the SITBI-SR or clinically significant increases in NSSI, a clinical risk assessment (including severity of ideation and presence of plan, intent, and access to means) will be conducted by a study clinician in order to ensure participant safety and that the

participant remains stable to be treated in an outpatient setting. After completing the post-treatment assessment, their study participation will be complete.

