Emotion Regulation Questionnaire (ERQ⁵⁵). The ERQ is a 10-item self-report measure assessing two emotion regulation strategies—cognitive reappraisal and expressive suppression. It will be used at the three assessment points to capture changes in emotion regulation during the study.

Brief Experiential Avoidance Questionnaire (BEAQ⁵⁶): The 15-item BEAQ is a modified, briefer version of the original 62-item Multidimensional Experiential Avoidance Questionnaire (MEAQ), self-report measure of six experiential avoidance domains: behavioral avoidance, distress aversion, procrastination, distraction/suppression, repression/denial, and distress endurance. It will be used at the three assessment time points to capture changes in experiential avoidance.

Overall Anxiety Severity and Impairment Scale (OASIS⁵⁷). This is a 5-item, self-report measure assessing the anxiety-related severity and impairment in the past week. It will be administered at each of the three assessment points to participants in both conditions. Participants in the UP + TAU condition will also complete it at the start of each UP session, per the treatment protocol³⁷.

Overall Depression Severity and Impairment Scale (ODSIS⁵⁸). This 5-item, self-report measure captures severity and impairment of depression in the past week. It will be administered at each of the three assessment points to participants in both conditions. Participants in the UP + TAU condition will also complete it at the start of each UP session, per the treatment protocol³⁷.

Self-Injurious Thoughts and Behaviors Interview-Clinician-Rated Version (SITBI-CR⁵⁰). This clinician-rated measure will be used to capture suicidal thoughts and behaviors and NSSI over lifetime, past year, past month, and past week at the screening/baseline visit.

Self-Injurious Thoughts and Behaviors Interview-Self-Report Version (SITBI-SR⁵⁰). This self-report measure will be used to capture suicidal thoughts and behaviors and NSSI in the past month at the mid-treatment and post-treatment assessments.

Timeline Follow Back (TLFB^{53,54}). The TLFB will be administered as an interview at all three time points in order to determine frequency and quantity of substance use, as well as percent days abstinent, since the last assessment (or at pre-treatment, over the past month). For the TLFB, participants mark the days on which they used a substance and indicate which substance(s) (and how much) they used.

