Specific Aim 2: Analyses will be intention-to-treat, such that participants will be analyzed as part of their allocated group irrespective how much treatment was received. Continuous variables (OASIS, ODSIS, BSI, CSS, and Craving Scale scores, frequency of NSSI urges and episodes captured by the SITBI, quantity and frequency of substance use, percent days abstinence [PDA]) will be analyzed with generalized mixed effect modeling, which imputes missing values based on maximum likelihood estimates of missing parameters (*Hypotheses 2a, 2b, 2c, 2d, 2e*). Time-by-condition interactions will be analyzed to test the efficacy of the adjunctive intervention. Known confounding variables (e.g., age, gender) will be included as covariates in these analyses. Effect sizes between the two conditions will also be reported. Although we will test for statistical significance, as previously noted, the primary aim of this pilot study is to estimate the intervention's effect size before conducting larger, more adequately powered future studies.

VII. RISKS AND DISCOMFORTS

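### Hypothesis 2c names a clinician-rated post-treatment NSSI endpoint that is never collected, and its planned test joins a baseline interview to follow-up self-report

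*Protocol*

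**What the plan says.** Protocol section II, Hypothesis 2c, concerns participants with past-month NSSI urges or episodes at baseline. It predicts that those in the UP arm will "report a lower frequency of NSSI urges and episodes in a one-month period on the Self-Injurious Thoughts and Behaviors Interview-Clinician Rated" "and on the Self-Injurious Thoughts and Behaviors Interview-Self-Rated" version at post-treatment than the control arm.

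The measure descriptions in section V give the two versions different visits. The SITBI-CR captures "suicidal thoughts and behaviors and NSSI over lifetime, past year, past month, and past week at the screening/baseline visit". The SITBI-SR captures "suicidal thoughts and behaviors and NSSI in the past month at the mid-treatment and post-treatment assessments". Table 1 agrees with both.

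The TAU condition paragraph of section V says of the mid-treatment visit that "they will complete the same self-report questionnaires (plus TLFB and concomitant treatment log with a study clinician) administered at the screening/baseline visit", and that the same measures are repeated at post-treatment. The UP + TAU arm has the same assessments plus the CSQ-8 and a feedback interview.

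Section VI, Specific Aim 2, lists among the outcomes for the generalized mixed model the "frequency of NSSI urges and episodes captured by the SITBI", with no version named. It then states: "Time-by-condition interactions will be analyzed to test the efficacy of the adjunctive intervention".

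**The concern.** Two things do not fit together.

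First, the hypothesis makes both versions the object of one post-treatment comparison, but only one of them is administered at that visit. The clinician-rated half of Hypothesis 2c cannot be reported.

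Second, a time-by-condition interaction meant to show efficacy needs a baseline value as its first time point. The only baseline NSSI value is a clinician interview, and every later value is a self-report form. A difference between interview and questionnaire reporting would then be read as change over time. It would enter any pre-post NSSI effect size, in a pilot whose stated purpose includes estimating effect sizes for later trials. It could also enter the between-arm comparison if it is not the same in both arms on the model's scale.

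The hypothesis and the test also differ in kind. Hypothesis 2c claims a lower post-treatment level, whereas 2a, 2b and 2d claim a greater pre-to-post change, which is what an interaction tests.

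**Working it through.** The Protocol gives no figure to reproduce here: it reports no formal power analysis, and nothing in this point depends on one. The check is a count from the schedule, followed by a short derivation.

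**Schedule (section V measure descriptions and Table 1)**

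| Version | Baseline | Mid-treatment | Post-treatment |
|---|---|---|---|
| SITBI-CR | yes | no | no |
| SITBI-SR | no | yes | yes |

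- Version-by-visit cells: 2 × 3 = 6. Scheduled: 1 + 2 = 3.
- Post-treatment endpoints named in Hypothesis 2c: 2. Collected: 1 (SITBI-SR).
- Versions with both a baseline and a post-treatment value: 0 of 2.
- Visits at which both versions are given: 0 of 3.

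The recall window is not the problem. The SITBI-CR includes a past-month period and the SITBI-SR covers the past month. What changes between baseline and follow-up is the mode.

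**Effect on the interaction.** Let μ be mean NSSI frequency on the interview scale, with U for UP + TAU, T for TAU, 0 for baseline and 1 for post-treatment. Let m be the shift from interview to self-report.

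- Within-arm change as observed: (μ1 + m) − μ0. The shift m cannot be separated from change.
- Interaction as observed: [(μU1 + mU) − μU0] − [(μT1 + mT) − μT0] = true interaction + (mU − mT).
- If mU = mT, the added term is 0 and the interaction is unbiased.
- If instead self-report is proportional to interview, with factor k in both arms, the interaction on an untransformed scale is k(μU1 − μT1) − (μU0 − μT0). This differs from the true interaction by (k − 1)(μU1 − μT1). On a log scale, log k cancels.

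So bias depends on whether the mode effect is constant on the scale of the model, and on whether it varies with severity or arm. Neither m nor k can be estimated, because no visit collects both versions.

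**Could the interaction be read without baseline as a time point?** With only the mid- and post-treatment SITBI-SR in the outcome, the time-by-condition term tests divergence between those two visits. A benefit already present at mid-treatment and simply maintained would give an interaction of zero. That is not a test of efficacy, so the stated test needs baseline in the outcome and therefore mixes modes.

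**The case against.** The strongest reply is that the intended use is evident: interview at baseline, where the subgroup is defined, and self-report at follow-up. The measure descriptions and Table 1 agree on this, and the SITBI-CR in the post-treatment clause looks like a drafting remnant. The self-report contrast at post-treatment, which is what Hypothesis 2c asks for, is fully collected. Which version enters the model, and how baseline is handled, could be settled in a SAP. Some of this stands: no scheduled data are lost, and the main defect is one of wording. But a SAP cannot supply clinician ratings that were never taken, and the Protocol itself fixes the interaction as the test.

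Section V also mentions clinician-rated measures at mid- and post-treatment that may be completed by phone. These are not the SITBI-CR: the TAU condition paragraph and Table 1 leave only the TLFB, the treatment log and adverse-event tracking as clinician items at follow-up. The clinician check at each visit in section IX concerns immediate suicide and homicide risk, not NSSI frequency.

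Three further points are fair:

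- The switch of mode is identical in both arms, so the interaction may well be unaffected.
- If reporting at follow-up differs by arm, a comparison on the SITBI-SR alone carries the same bias, and the fix does not remove it.
- The mismatch between level and change also applies to Hypothesis 2e, so it is partly a general matter of how section VI is worded.

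The TAU condition sentence is a loose summary that refers the reader to the measure descriptions. Its implication of a baseline SITBI-SR is minor.

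**Conclusion.** The point holds. One of the two post-treatment endpoints named in Hypothesis 2c cannot be observed, and the stated efficacy test for NSSI pairs a clinician interview with self-report. Within-arm NSSI change cannot be interpreted. Any bias in the between-arm interaction is of unknown size. It is zero if the mode shift is constant on the model's scale and the same in both arms, an assumption the trial has no data to check.

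The consequence is limited: this is one exploratory Aim 2 outcome, in a baseline-defined subgroup of a 50-person pilot with no formal power calculation. It should be corrected before analysis, but it does not threaten the trial's main aims. The conclusion rests on Table 1 and the measure descriptions being the schedule actually followed.

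**What to change.** - **Hypothesis 2c:** remove the SITBI-CR from the post-treatment endpoint, leaving past-month NSSI urges and episodes on the SITBI-SR. Keep the SITBI-CR for eligibility and for defining the subgroup with past-month NSSI at baseline.
- **Section VI, Specific Aim 2:** name the version. State that SITBI-SR frequency at mid- and post-treatment is compared between arms, with terms for condition, visit and their interaction, and with baseline past-month SITBI-CR frequency as a covariate and not as the first time point. State that the condition contrast at post-treatment answers Hypothesis 2c. A pre-randomization covariate need not share the outcome's mode, so the model no longer treats interview and questionnaire as one scale, and the test then matches the hypothesis's claim about level.
- **Section V, TAU condition:** reword the follow-up sentence so that it does not imply a baseline SITBI-SR.

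The cost is wording in three places. The analysis uses only data already scheduled, so it applies to every participant in the subgroup. A baseline SITBI-SR is not needed.

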The UP was originally designed as a time-limited, CBT protocol to be delivered in 12 to 16 individual outpatient therapy sessions³⁷. Previous studies have demonstrated that the original UP can be successfully modified for administration in other formats (e.g., 12 2-hour weekly outpatient group sessions⁶⁰, 5 one-hour individual inpatient sessions¹⁹). For this study, the UP will be delivered over the course of 16, 1-hour twice-weekly sessions, delivered over an 8-week period, in order to be consistent with the length of existing group treatment session (1 hour) and average group treatment engagement (8 weeks) at ARMS.

Each of the original 8 UP modules (motivation enhancement, functional assessment of emotions, mindful emotion awareness, cognitive flexibility, countering emotion-driven behaviors, interoceptive exposure, emotion exposure, relapse prevention³⁷) will be delivered to a small group of up to 10 participants. See Table 2 for weekly session content. One UP group will be running at any point in time within ARMS, Admission will be partially rolling, such that new study participants can enter the group intervention at any point through UP Week 5 (and then, for example, would attend UP Weeks 1-4 after UP Week 8). If a participant beginning the group treatment during UP Week 5 misses one of the two UP Week 5 sessions, they will undergo an individual "catch-up" session before UP Week 6 in order to ensure that they have received all the UP Week 5 material before proceeding to UP Week 6. Participants will not be permitted to begin the group during UP Weeks 6-8 as these sessions (interoceptive and emotion exposure exercises) are contingent upon learning the emotion management skills presented during UP Weeks 1-5. Should a group of five participants be randomized to the UP + TAU condition during UP Weeks 6-8, they will wait up to attend their first UP group session until UP Week 1 begins again (up to

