Week 7	Session 14	No	Emotion exposure (UP Module 7):
			-Present the rationale for conducting emotion exposure
	(Repeat		exercises (including the natural course of emotion)
	Session 12)		-Conduct emotion exposure exercise as a group (e.g.,
			imagining an emotional situation, listening to emotion-
			provoking music, or watching an emotional video
			while practicing new emotion management skills)
Week 8	Session 15	No	Relapse prevention (UP Module 8):
			-Review key treatment concepts and emotion
			management skills
			-Identify ongoing opportunities for skills practice
			-Identify long-term goals
Week 8	Session 16	No	Relapse prevention (UP Module 8):
			-Review key treatment concepts and emotion
			management skills
			-Identify ongoing opportunities for skills practice
			-Identify long-term goals
L	1		

VI. BIOSTATISTICAL ANALYSIS

Power: The proposed pilot study is the first, necessary step in obtaining preliminary data to justify future larger, randomized trials. Although we will test for statistical significance, the primary aim is to obtain usable feasibility and acceptability data, as well as to estimate the adjunctive intervention's effect size in order to conduct more adequately powered studies in the future. As such, a formal power analysis was not conducted *a priori*; however, the proposed N (50 subjects) is in line with other recent pilot RCTs examining the feasibility and preliminary efficacy of cognitive-behavioral group interventions for young adults⁶¹ and teens⁶² with SUD.

Preliminary analyses will describe the participants' demographic and clinical characteristics. Comparisons will be made using Mann-Whitney or chi-square tests to determine if the

randomization provided a balanced sample and if participants who dropped out differ from those who did not. All analyses will be conducted using the SPSS and/or Stata statistical packages.

Specific Aim 1: We will use descriptive statistics to report satisfaction ratings with the UP intervention (total CSQ-8 score; *Hypothesis 1a*) and number of UP sessions attended. We will use chi-square tests to evaluate differences in the proportion of participants in each condition who drop out of treatment at the ARMS program during the study period (*Hypothesis 1b*).

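### Whole groups of five are randomised (10 units for N = 50), but no analysis the protocol names accounts for the group, so precision is overstated if group members are correlated

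*Protocol*

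**What the plan says.** Section IV. Subject Enrollment labels the allocation a permuted block procedure and then describes something else. Groups "of 5 individuals will be randomized at a time to one of the two treatment conditions". The 2:1 ratio is "defined as 2 blocks randomized to UP + TAU for every 1 block randomized to TAU alone", and the code is generated only "once the last participant of each group has completed baseline". The description of the UP treatment in section V agrees; it opens a waiting rule with "Should a group of five participants be randomized to the UP + TAU condition during UP Weeks 6-8". The same section says "One UP group will be running at any point in time within ARMS", with up to 10 members and partially rolling entry.

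Section VI. Biostatistical Analysis works at participant level. For Hypothesis 1b: "We will use chi-square tests to evaluate differences in the proportion of participants in each condition". For Aim 2 it names a generalized mixed effects model: "Time-by-condition interactions will be analyzed to test the efficacy of the adjunctive intervention", and "Known confounding variables (e.g., age, gender) will be included as covariates in these analyses". The section mentions no group, block or cluster term and does not state the model's random effects.

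**The concern.** Permuted blocks normally means that individuals are allocated within a block. Here the block itself is allocated, and all five members receive the same condition. A block of five could not contain a 2:1 split anyway (5 × 2/3 = 3.33). The randomised unit is the group, so the design is a small cluster-randomised trial.

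Some within-group correlation is plausible. Groups in both arms fill in order of enrolment, so members share a calendar period, and UP members also share therapy sessions. If the correlation is above zero, participant-level tests give p-values that are too small and intervals that are too narrow. This matters even in a pilot, because section VI says that significance will be tested and that a main purpose is to estimate an effect size for later trials. The block label makes the error likely to persist, since an analyst who reads it would take individuals as the unit.

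**Working it through.** **Inputs from the protocol.** N = 50; groups of m = 5; 2:1 defined on groups; chi-square for dropout; mixed model with time-by-condition and person-level covariates. No power calculation, ICC, significance level or dropout rate is given, so there is no stated figure to reproduce.

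**Assumptions.** ICC 0 to 0.20, two-sided 5% level, 30% dropout.

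**1. Number of units.** 50/5 = 10 groups. Exact 2:1 would need 10 × 2/3 = 6.67 groups, so the nearest splits are 7:3 (35 v 15 people) or 6:4 (30 v 20).

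**2. Analytic size.** The design effect is DE = 1 + (m − 1) × ICC = 1 + 4 × ICC. The standard error is understated by √DE, and the true size of a nominal 5% z-test is 2 × [1 − Φ(1.96/√DE)].

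| ICC (both arms) | DE | Effective N (50/DE) | √DE | True size |
|---|---|---|---|---|
| 0 | 1.00 | 50.0 | 1.00 | 5.0% |
| 0.01 | 1.04 | 48.1 | 1.02 | 5.5% |
| 0.05 | 1.20 | 41.7 | 1.10 | 7.4% |
| 0.10 | 1.40 | 35.7 | 1.18 | 9.8% |
| 0.20 | 1.80 | 27.8 | 1.34 | 14.4% |

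**3. Simulation.** 40,000 null trials per setting, 7:3 split, dropout drawn from a beta-binomial distribution. Entries are rejection rates at nominal 5%.

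| ICC | t-test, both arms | Uncorrected chi-square, both arms | Continuity-corrected chi-square, both arms | t-test, UP only | Uncorrected chi-square, UP only |
|---|---|---|---|---|---|
| 0 | 4.9% | 4.9% | 2.2% | – | – |
| 0.01 | 5.5% | 5.7% | 2.6% | – | – |
| 0.05 | 7.2% | 7.5% | 3.7% | 5.9% | 5.8% |
| 0.10 | 9.8% | 9.8% | 5.3% | 6.4% | 6.6% |
| 0.20 | 14.7% | 15.0% | 8.9% | 8.0% | 8.3% |

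The 6:4 split gives similar t-test results (7.5/10.0/14.6% at ICC 0.05/0.10/0.20, both arms). If the ICC is defined on a latent normal scale, the correlation between binary outcomes is smaller and the uncorrected chi-square at 7:3 rejects 5.2/6.3/7.6/10.7% at ICC 0.01/0.05/0.10/0.20. A t-test on group values holds 4.7% to 5.3% when both arms share the same ICC.

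**4. Aim 2.** A time-by-condition test compares change, so the relevant ICC is that of change. With within-person correlation 0.5 and a 7:3 split, a stable group difference cancels (4.9% to 5.1%). An ICC of change of 0.05/0.10/0.20 gives 7.2/9.7/14.9% if the model has no group term.

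**5. Interval width at 35 v 15.** SE of a standardised difference = √(1/35 + 1/15) = 0.309.
- Groups ignored: 1.96 × 0.309 = 0.60 with z, or 2.011 × 0.309 = 0.62 with t on 48 df.
- Group level, ICC 0: 2.306 × 0.309 = 0.71 (t on 8 df).
- Group level, ICC 0.05/0.10/0.20: 0.71 × √DE = 0.78/0.84/0.95.

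The step from 0.62 to 0.71 is the cost of having 8 df. Only the further widening comes from correlation.

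**The case against.** The strongest reply concerns Aim 2. A mixed model can carry a group random effect, the covariate list is only illustrative, and random-effects structure is commonly left to a statistical analysis plan, which is not available here. That stands: for Aim 2 the concern is conditional. It does not cover Hypothesis 1b, where the protocol itself fixes a participant-level test that cannot account for the group.

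The size is also uncertain. TAU is individualised and nothing says that a TAU five ever meets, so the shared-session mechanism is documented in the UP arm only, where inflation is smaller. The protocol does not say whether the chi-square is continuity-corrected. At 30% dropout the 15 controls give an expected count of 15 × 0.30 = 4.5, where a corrected or exact test is often chosen, and the corrected test stays below 5% up to an ICC of 0.05. These points are right and limit the magnitude. Shared enrolment period still makes some correlation in TAU possible.

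Pilot status lowers the weight of the significance tests, but not of the interval around the effect size.

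Finally, the randomised five is not the therapy group. With one rolling group of up to 10, successive fives can share sessions, and a random effect for the randomised five does not capture that overlap. This limits the remedy but does not justify ignoring the group.

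**Conclusion.** The concern holds. The protocol randomises 10 groups, not 50 individuals; it fixes a participant-level test for dropout and names no group term elsewhere. The effect size is not biased, but its uncertainty is understated if the ICC is above zero.

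The amount depends on an ICC that the document does not give. Inflation is absent at 0, negligible at about 0.01, modest if only the UP arm is correlated, and material from about 0.05 if both arms are. For Hypothesis 1b it also depends on the dropout rate and on the continuity correction. For Aim 2 it depends on whether groups differ in change and whether the fitted model includes a group term.

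**What to change.** - **Randomisation text.** Reconcile the block label with whole-group assignment, and state the attainable split (7:3 or 6:4).
- **Hypothesis 1b.** Replace the chi-square test with a t-test on group dropout proportions (10 − 2 = 8 df) or a permutation test over groups that follows the actual schedule. Unrestricted, a 7:3 split has 120 arrangements. If the schedule permutes groups in threes (an assumption), only 3 × 3 × 3 = 27 remain.
- **Aim 2.** Include randomisation group as a random effect with small-sample degrees of freedom. Where it cannot be estimated (as few as 3 control groups, or the subsets for Hypotheses 2b and 2c), analyse change at group level.
- **Reporting.** Give between-condition effect sizes with group-adjusted intervals. Note that UP groups sharing sessions may be further correlated. Do not plan a later trial on this pilot's ICC alone: at a true ICC of 0.10, the estimate from 10 groups has a 95% sampling range of −0.14 to 0.37 and is at or below zero 26% of the time.

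**Cost.** Only the wording changes, because group membership is already known. Intervals widen and apparent power falls. For a standardised difference of 0.8 at 35 v 15, power is 72% if groups are ignored, 62% at group level with ICC 0, and 49% at ICC 0.10. If correlation exists only in the UP arm, the group-level t-test is somewhat conservative at 7:3 (4.2/3.9/3.0% at ICC 0.05/0.10/0.20).
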